## **I. Administrative information:**

### **1. Title:**

Evaluation of the Chemo-preventive effect of Combined Topical and Systemic Metformin on Oral Leukoplakia: A Randomized Clinical Trial

### **2. Date of Submission to clinical trials:**

12/9/2025

### **3. Date of Ethical Approval:**

April 2021

### **4. Protocol Registration:**

The protocol is being registered on clinicaltrial.gov

### **5. Protocol version:**

This protocol has only one version (the one submitted)

### **6. Funding:**

Self-Funded

## **I. Introduction**

### **1. Background and rationale:**

#### **Research question:**

In patients with oral mucositis, will MEBO result in clinical improvement as compared to Benzydamine Hydrochloride spray?

#### **PICO:**

Population [P]: patients with oral mucositis attending the National Cancer Institute clinic

Intervention [I]: MEBO

Comparison [C]: Benzydamine Hydrochloride spray

Outcome [o]: clinical improvement and quality of life

Outcome measure		Method of measurement	Unit of measurement
1 ry Outcome	Clinical improvement	World Health Organization (WHO)scale.(1)  Oral Mucositis Assessment Scale (OMAS).(2)	Ordinal
2 ry Outcome	quality of life	Patient-Reported Oral Mucositis( PROMS scale).(3)	Continuous outcome (Score codes).

#### **Statement of the problem:**

Oral mucositis (OM) refers to mucosal damage secondary to cancer therapy occurring in the oral cavity. Mucositis can be caused by chemotherapy and/or radiation therapy. It occurs in approximately 20% to 40% of patients receiving conventional chemotherapy, 80% of patients receiving high dose chemotherapy as conditioning for hematopoietic stem cell transplantation, and nearly all patients receiving head and neck radiation therapy. OM can disturb speaking and eating, resulting in nutritional deficiency.(4)

The management of oral mucositis is a challenge, due to its complex biological nature. Over the last 10 years, different strategies have been developed for the management of oral mucositis.(5)

#### **Rationale for conducting the research:**

Oral mucositis consequences can range from pain, decreased oral intake, impaired speech and swallowing to adverse events as severe as septicemia, increased hospitalization, and G-tube feeding (6)

A wide variety of agents have been tested to prevent OM or reduce its severity.(7) This trial will assess the usefulness of MEBO versus Benzylamine Hydrochloride mouth wash in management of oral mucositis in patients receiving radiotherapy and/or chemotherapy.

### **Background:**

The term “mucositis” was introduced to describe inflammation of the oral mucosa induced by radiotherapy, chemotherapy and bone marrow transplantation. At present, oral mucositis is considered to be the most serious non-hematological complication of cancer treatment.(8)

Numerous predisposing factors have been blamed for oral mucositis, including: the type of tumor involved, age of the patient, dental health, the nutritional condition of the patient, the maintenance of kidney and liver function and the type of cytostatic agent used.(9)

Clinically, oral Mucositis may appear as erythema, edema or ulceration that can be accompanied by alterations ranging from mild burning sensation to large and painful ulcers that worsen patient's quality of life and limit basic oral functions such as speech, swallowing of saliva or eating.(10)

According to Multinational Association for Supportive Care in cancer and the International Society of Oral Oncology (MASCC/ISOO) guidelines for the management of mucositis, Management of oral mucositis is divided into the following sections: nutritional support, pain control, oral decontamination, palliation of dry mouth, management of oral bleeding and therapeutic interventions for oral mucositis.(11)

Since the primary symptom of oral mucositis is pain which significantly affects nutritional intake, mouth care and quality of life, thus, management of mucositis pain is a primary component of any mucositis management strategy. Use of saline mouth rinses, ice chips and topical mouth rinses containing an anesthetic such as 2% viscous lidocaine can help in reducing pain (12)

Based on the pathogenesis of mucositis with complex biological inflammatory pathways, various therapeutic approach have been proposed to improve oral mucositis.(13)

The current guidelines recommend the use of non-medicated oral rinses such as Benzylamine hydrochloride mouthwash and the use of short-term pain killers. Benzylamine hydrochloride - which is a non-steroidal anti-inflammatory drug - can be used in the form of mouth rinse to reduce the severity of oral mucositis. Other management strategies include cryotherapy before the start of chemotherapeutic agent administration and application of low-level

laser therapy. Palifermin (Keratinocyte growth factor) is the only recommended preventive measure recommended by the ESMO Clinical Practice Guidelines.(14)

## **7. Objectives**

### **Aim of the study:**

To assess the effect of MEBO versus Benzylamine Hydrochloride spray regarding clinical improvement of oral mucositis and quality of life of patients receiving radiotherapy and/or chemotherapy

## **8. Study design:**

Phase III Randomized clinical trial (parallel arms)

## **II. Materials and Methods**

### **Participants:**

#### **9. Study settings:**

The patients will be selected from the pool of the Out-Patient Clinic of National Cancer Institute

**Population:** A random sample of adult patients receiving radiotherapy and having sign and symptoms of oral mucositis

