#### **10. Eligibility criteria:**

##### **A- Inclusion criteria:**

- 1) Patients having clinical signs of chemotherapy-induced or radiotherapy-induced OM (WHO oral mucositis grading scale: Grade II, III and IV)
- 2) Patients over the age of 18 years
- 3) Patients having no history of allergy, allergic rhinitis and asthma

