### Application Form

#### Human Subjects

##### Kindly fulfill the following:

##### **Research title:**

Clinical Evaluation of MEBO Versus ~~Benzydamine~~ Hydrochloride In Management of Patients with radiotherapy induced Oral Mucositis: Randomized Clinical Trial

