##### **Research objective:**

To assess the effect of MEBO versus ~~Benzydamine~~ Hydrochloride spray regarding clinical improvement of oral mucositis and quality of life of patients receiving ~~radiotherapy~~

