##### **• Research Procedure in brief:**

A random sample of adult patients receiving radiotherapy or chemotherapy and having sign and symptoms of oral mucositis and this. Enrolled patients will be divided randomly into two groups, each consists of 21patients.

**Intervention group:** Patients will receive MEBO three times daily for two week

**Control Group:** Patients will receive ~~Benzydamine~~ Hydrochloride spray three times daily

**Follow up:** The patients will be recalled at one week interval for two week

as there is no treatment of oral mucositis available in Egyptian market

We will offer palliative treatment that will alleviate the pain of oral mucositis

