##### **value and social benefits:**

treatment of chemotherapy and radiotherapy induced oral mucositis

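### Section 9 and the application form title describe radiotherapy patients, but the eligibility criteria, aim and rationale also admit chemotherapy patients, and nothing says which description governs

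*Combined protocol and SAP*

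**What the plan says.** Two places, and possibly a third, name radiotherapy alone:

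- Protocol section 9, under Population: "A random sample of adult patients receiving radiotherapy and having sign and symptoms of oral mucositis".
- Application form, Research title: "Management of Patients with radiotherapy induced Oral Mucositis".
- Application form, Research objective: "clinical improvement of oral mucositis and quality of life of patients receiving ~~radiotherapy". The last word carries strike-through marks in the extracted text, so this entry is uncertain.

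Five places also admit chemotherapy:

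- Protocol, Rationale: "management of oral mucositis in patients receiving radiotherapy and/or chemotherapy".
- Protocol section 7, Aim of the study: "quality of life of patients receiving radiotherapy and/or chemotherapy".
- Protocol section 10, inclusion criterion 1: "Patients having clinical signs of chemotherapy-induced or radiotherapy-induced OM".
- Application form, Research Procedure in brief: "A random sample of adult patients receiving radiotherapy or chemotherapy and having sign and symptoms of oral mucositis".
- Application form, value and social benefits: "treatment of chemotherapy and radiotherapy induced oral mucositis".

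The research question, the PICO table and section 15 (Recruitment) speak of oral mucositis without naming a cancer treatment. Section 16a specifies simple randomisation. Section 20 compares the groups by t-test or Mann-Whitney test and names no covariate.

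**The concern.** The entry population decides whom the result applies to. Someone reading section 9 or the form title would expect a trial in radiotherapy patients. Someone applying section 10 would enrol patients whose mucositis came from chemotherapy alone. If the mix is neither settled nor reported, a reader cannot tell which of these trials was run.

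The protocol's problem statement treats the settings as distinct. It gives mucositis in roughly 20% to 40% of patients on conventional chemotherapy, 80% on high-dose conditioning chemotherapy, and nearly all patients receiving head and neck radiation.

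The randomisation is not stratified and the analysis is not adjusted, so nothing in the plan takes account of the cause of mucositis or of its severity at entry.

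**Working it through.** **Who falls where.** Taking section 9 and criterion 1 as written, for a patient with mucositis of the required grade:

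| Patient's cancer treatment | Section 9 population | Section 10, criterion 1 |
|---|---|---|
| Radiotherapy alone | inside | eligible |
| Radiotherapy with chemotherapy | inside | eligible |
| Chemotherapy alone | outside | eligible |

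The conflict is confined to the last row.

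**The struck word in the form's objective.** The same marks fall on the comparator's name in the form's title, objective and procedure, so they are probably an extraction artefact. If the deletion were real, the objective would name no treatment, and section 9 and the form title would still conflict with section 10.

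**The plan's own sample size.** Section 14 gives effect size 1.011, power 80%, alpha 5%, 1:1 allocation and 17 per group. Assuming a two-sided two-sample t-test, the exact calculation gives 16.38, rounded up to 17, with power 81.5% at that size. The figure reproduces. The documents do not say which cancer treatments the patients in the cited study had, so the effect of the population choice on this number cannot be computed.

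**Patients affected.** Section 14 implies 2 × 17 = 34 patients, the application form 2 × 21 = 42, and sections 11 and 13 2 × 33 = 66. The chemotherapy-only share p is not given; assume 10-50%.

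- N = 34: 3.4 to 17
- N = 42: 4.2 to 21
- N = 66: 6.6 to 33

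**Timing.** Section 15 starts recruitment in January 2022 and section 11 expects one year, so planned enrolment ended about January 2023. The submission date, 12/9/2025, is 32 or 35 months later (September or December, depending on day/month order).

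**Cost of one covariate.** Under simple randomisation the expected standard error (SE) is multiplied by √((N−3)/(N−4)):

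- N = 34: √(31/30) = 1.017
- N = 42: √(39/38) = 1.013
- N = 66: √(63/62) = 1.008

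**Adjusting for the baseline score.** The SE is multiplied by √(1−r²), with r the assumed baseline-outcome correlation.

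| r | Before cost | Net, N = 34 | Net, N = 66 |
|---|---|---|---|
| 0.3 | 0.954 (5% lower) | 0.970 (3% lower) | 0.962 (4% lower) |
| 0.5 | 0.866 (13% lower) | 0.880 (12% lower) | 0.873 (13% lower) |

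**Adjusting for cause.** If cause shifts the score by δ within-cause standard deviations (assumed 0.5-1.0), leaving it out multiplies the SE by √(1 + p(1−p)δ²). Dividing by the covariate cost gives the net ratio of unadjusted to adjusted SE. Values above 1 favour adjustment.

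| p, δ | Before cost | N = 34 | N = 42 | N = 66 |
|---|---|---|---|---|
| 0.1, 0.5 | √1.0225 = 1.011 | 0.995 | 0.998 | 1.003 |
| 0.5, 1.0 | √1.25 = 1.118 | 1.100 | 1.104 | 1.109 |

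The net effect runs from a loss of about 0.5% to a gain of about 11%. These formulas are for a linear model; for an ordinal model they are only indicative.

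**The case against.** The strongest reply is that this is one loose line. Within the protocol body only section 9 is out of step. It sits under study settings, does not say that chemotherapy patients are excluded, and covers patients on combined treatment. Section 10 is the working entry rule and agrees with the aim and rationale, so an investigator following it would enrol both causes. The application form is a separate submission from the protocol text. Much of this stands, and it limits the weight of the point. It does not remove it: section 9 is labelled as the population, the form title takes the narrower reading independently, and no text gives section 10 precedence.

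Three stronger readings are tempting, and the documents support none of them.

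- *Ignoring cause in section 20 biases the comparison.* Treatment is randomised, so leaving cause out can cost precision but does not bias the comparison.
- *The problem statement shows that cause changes the outcome.* Its percentages concern how often mucositis occurs, not how it responds to treatment. The 80% for high-dose chemotherapy also narrows the contrast with radiation.
- *Since most passages include chemotherapy, the narrower ones should simply be widened.* A count of passages does not show what was intended. If only radiotherapy patients were enrolled, widening would misdescribe the trial.

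It is also fair to object that adjusting for cause is a matter of preference. At the smaller totals and the low end of the assumptions it costs slightly more than it gains.

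**Conclusion.** The contradiction holds and can be checked from the text alone. Section 9 and the form title, together with the form objective if its marked word stands, describe a narrower population than section 10, the aim, the rationale and the rest of the form. Patients on chemotherapy alone are eligible but outside the stated population. It should be corrected because it settles whom the result covers; it is not a reason to regard the comparison as invalid.

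The numerical sizes rest on assumptions that the documents neither support nor contradict: the chemotherapy-only share, the shift by cause and the baseline correlation. The total sample size is itself stated three ways. Under those assumptions baseline adjustment helps throughout the range, while adjustment for cause ranges from slightly harmful to useful. That enrolment may be over is inferred from planned dates only.

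**What to change.** 1. **State one population.** Reconcile section 9 and the form's title and objective with the rationale, the aim, section 10 and the form's procedure and benefits text. First establish from the records who was enrolled. If enrolment is over, the stated population must match those patients and be entered as a dated amendment by the route in section 22 (Protocol amendments). Report counts by cause (radiotherapy with or without chemotherapy; chemotherapy alone) and by arm.

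2. **Adjust for baseline in section 20.** Include the baseline value of the same score in the between-group comparison: a linear model for PROMS and an ordinal model for the WHO grade. Section 10 requires a WHO grade at entry, and section 12 schedules PROMS at baseline. If outcomes by arm have already been seen, label this analysis supportive.

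3. **Optional.** Add cause as a covariate if both causes were enrolled in reasonable numbers, with the same labelling.

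The cost is a few wording edits, the amendment entry, and one item per patient taken from existing records. No extra patients or visits are needed. Each covariate costs about 0.8% of the standard error at N = 66 and 1.7% at N = 34, before any gain.

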#### **10. Eligibility criteria:**

##### **A- Inclusion criteria:**

- 1) Patients having clinical signs of chemotherapy-induced or radiotherapy-induced OM (WHO oral mucositis grading scale: Grade II, III and IV)
- 2) Patients over the age of 18 years
- 3) Patients having no history of allergy, allergic rhinitis and asthma

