##### **B- Exclusion criteria:**

- 1) Patients allergic to the used treatment
- 2) Patient receiving systemic steroids
- 3) Patients who don't approve to participating in the clinical trial.

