#### **11. Interventions:**

**Enrolment:** Enrolment is expected to be done within a one-year period. The enrolled patients will be divided randomly into two groups, each consisting of 33 patients.

**Intervention group:** Patients will receive mixture of MEBO three times daily for 14 days

**Control Group:** Patients will receive Benzydamine Hydrochloride spray three times daily for 14 days.

**Follow up:** The patients will be recalled at one week interval for 14 days.

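### Timing of cancer therapy is not set at entry, and no section plans to record or adjust for it, which costs precision and leaves chance imbalance uncheckable

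*Combined protocol and SAP*

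**What the plan says.** Several sections describe the population as people on cancer therapy:

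- Section 7, Aim of the study: "quality of life of patients receiving radiotherapy and/or chemotherapy". The rationale paragraph in the Introduction agrees.
- Section 9, Study settings: "adult patients receiving radiotherapy and having sign and symptoms of oral mucositis".
- Application Form, Research Procedure in brief: "A random sample of adult patients receiving radiotherapy or chemotherapy and having sign and symptoms of oral mucositis".

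The entry rule itself is different. Section 10 A, criterion 1, requires "Patients having clinical signs of chemotherapy-induced or radiotherapy-induced OM" with WHO grade II, III or IV. It asks what caused the mucositis, not whether the cause is still acting. The other inclusion criteria cover age and allergy history. The exclusions cover allergy to the study treatment, systemic steroids and refusal. None mentions finished, ongoing or scheduled therapy.

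On follow-up, section 11 says "The patients will be recalled at one week interval for 14 days". Section 18 lists outcome data as questionnaires, pictures and written grading. Section 26 mentions demographic, clinical and analytical data without itemising them. Section 16a specifies simple 1:1 randomisation. Section 20 compares the arms with a t-test or Mann-Whitney test and names no covariate.

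**The concern.** The Statement of the problem names chemotherapy and radiation as causes of mucositis. Whether that cause is still acting during a 14-day assessment is a plausible prognostic factor for the WHO grade and the PROMS score. A patient past the end of a course may heal unaided, while one with further fractions or a new cycle in the window may be injured again.

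Two things are at stake. First, the target population is unclear: a patient with a finished course meets criterion 1 but lies outside the aim. Second, if status is not recorded, its contribution to outcome variance stays in the error term, and nobody can check afterwards whether the arms were alike on it. The trial is open-label (section 17), so readers will want to see that comparison.

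**Working it through.** **The plan's own figure.** Section 14 gives an effect size of 1.011, 80% power, 5% alpha, 1:1 allocation and 17 per group. A two-sided two-sample t-test (noncentral t) needs 16.4, rounded up to 17, so the figure is reproduced. At d = 1.011, power is 81.5% with 17 per arm (section 14), 89.2% with 21 (Application Form) and 98.1% with 33 (sections 11 and 13). All three sizes are carried below because the document gives all three.

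**Assumptions, not in the documents.** A share p of patients is off therapy, with p = 0.3 to 0.5. Off-therapy patients score better at day 14 by b within-stratum SDs, with b = 0.5, 1 or 1.5. The planning value 1.011 is taken as free of this factor.

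**Variance explained.** With within-stratum variance 1, the total variance is 1 + b²p(1−p), and R² = b²p(1−p) / [1 + b²p(1−p)].

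- Lowest: p = 0.3, b = 0.5 gives 0.0525 / 1.0525 = 5.0%.
- Middle: b = 1 gives 0.21 / 1.21 = 17.4% (p = 0.3) and 0.25 / 1.25 = 20.0% (p = 0.5).
- Highest: p = 0.5, b = 1.5 gives 0.5625 / 1.5625 = 36.0%.

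Removing this variance by adjustment is worth b²p(1−p) in extra patients: 5–6%, 21–25% and 47–56% for the three gaps.

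**Power of the unadjusted t-test.** The effect size becomes 1.011 / √[1 + b²p(1−p)].

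| p | b | effect size | n per arm for 80% | power, 17 | power, 21 | power, 33 |
|---|---|---|---|---|---|---|
| – | 0 | 1.011 | 17 | 81.5% | 89.2% | 98.1% |
| 0.3 | 0.5 | 0.985 | 18 | 79.6% | 87.6% | 97.6% |
| 0.3 | 1 | 0.919 | 20 | 73.8% | 82.8% | 95.7% |
| 0.3 | 1.5 | 0.833 | 24 | 65.4% | 75.0% | 91.5% |
| 0.5 | 0.5 | 0.981 | 18 | 79.2% | 87.3% | 97.5% |
| 0.5 | 1 | 0.904 | 21 | 72.5% | 81.6% | 95.1% |
| 0.5 | 1.5 | 0.809 | 25 | 62.8% | 72.5% | 89.9% |

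**Chance imbalance.** With two independent binomials of size n, the probability that the off-therapy shares differ by 20 percentage points or more, for p = 0.3 and 0.5, is:

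- 17 per arm: 18.9% and 22.9%
- 21 per arm: 12.8% and 16.4%
- 33 per arm: 8.0% and 10.9%

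A 20-point imbalance shifts the unadjusted difference by 0.2b, that is 0.1, 0.2 or 0.3 SD. For b = 1 at 33 per arm, the standard error of the difference is √(2/33) × √1.21 = 0.27 to √(2/33) × √1.25 = 0.28 SD. The 0.2 SD shift is therefore less than one standard error.

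**The case against.** The strongest reply is that sections 7 and 9 and the Application Form all speak of patients on therapy, so criterion 1 should be read with them. A reader might infer that the trial sets out to admit patients at any time during or after therapy. The documents do not say so; criterion 1 is simply silent. If section 9 governs, much of the assumed mix at entry disappears. What stands is that the criterion does not carry the restriction, and that being on therapy at entry does not settle what happens over the next 14 days.

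A reader might also infer that therapy data will not be collected. That too is silence: section 18 lists outcome data only, and section 26 leaves clinical data unitemised. Even if the data are collected, section 20 does not use them.

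The tempting stronger reading is that the arm difference will partly measure who was still being treated. Under 1:1 randomisation the expected contribution is zero and either arm is equally likely to benefit. Chance imbalance is already in the standard error, so the test keeps its type I error.

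The size is also open to challenge. The documents say that therapy causes mucositis but give nothing on its 14-day course on versus off therapy, so they do not establish a major driver. The lowest case, 5% of variance, is as admissible as the highest. If the study behind 1.011 enrolled a similar mix, its SD already contains the factor and the plan loses no power relative to its own calculation.

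**Conclusion.** The point holds as a matter of precision and of a clearly stated population, not as a flaw that invalidates the comparison. The entry criterion and the population statements disagree on whether therapy must be ongoing. No available section plans to record therapy status, and the analysis makes no use of it.

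Under the assumed ranges the factor explains about 5–36% of outcome variance. If 1.011 is free of it, power at 33 per arm falls from 98% to 90–98%, a modest loss; at 17 per arm it falls from 81.5% to 63–80%, which matters. The share off therapy, the gap and the SD are all assumed. The population mismatch and the inability to check balance afterwards do not depend on those values. The change is worth making because it is cheap and because therapy during follow-up is best logged as it happens.

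**What to change.** 1. Reconcile criterion 1 with section 7, section 9 and the Application Form by stating whether patients with finished courses belong to the target population. That choice is for the investigators.
2. At baseline, before the allocation envelope is opened, log from the clinic record whether therapy is ongoing or scheduled within the next 14 days (yes/no). This wording also classifies patients between chemotherapy cycles, whom an ongoing/finished split would leave out.
3. At weeks 1 and 2, log therapy delivered or paused.
4. Replace the unadjusted between-arm test of the day-14 score with a pre-specified regression that includes the baseline status: ANCOVA for a score, or an ordinal model for the WHO grade.
5. Report therapy after randomisation by arm, descriptively. Do not adjust for it, since it could be affected by the allocated treatment.

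The cost is a few form fields taken from existing records, one degree of freedom, and a regression model in place of the t-test or Mann-Whitney test. Cancer care is unchanged.
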